7.4 Interim Analyses

Two interim analyses will be performed to list, tabulate and plot all available data by the planned data cut off to assess the efficacy and safety of the investigation product (OTL-103). The approximate schedules of the interim analyses are as follows:

1. When the first 6 treated subjects complete 3 years of follow up after gene therapy as committed in the European PIP.
2. After the clinical database for marketing authorization application is locked

7.5 Multiple Testing

As the primary and secondary analyses are not powered for, there will be no adjustment for multiplicity across the primary and secondary endpoints.

8 Summary of Study Data

There is only one treatment group and the label used on outputs will be 'OTL-103'.

In general, continuous variables will be summarized using the following descriptive summary statistics: n (non-missing sample size), mean, SD, median, minimum and maximum. However, certain variables will additionally have geometric mean and geometric CV (coefficient of variation) presented.

For categorical measures, the frequency and percentages of observed levels will be reported.

Further details will be specified in a separate shells document. The shell templates provided will describe the presentations for this study and therefore the format and content of the summary tables, figures, and listings to be provided in accordance with the recommendations in ICH E3.

Unless otherwise specified, study population and efficacy outputs will use the ITT population and safety outputs will use the mobilisation set.

8.1 Subject Disposition and Protocol Deviations

All subjects who provide informed consent will be accounted for in this study.

Subject disposition and withdrawals, duration of follow-up and protocol deviations, including inclusion and exclusion criteria will be presented for the ITT set.

Summary statistics for the duration of follow-up will be presented and individual durations listed. Listings will be created for reasons for withdrawal, protocol deviations and inclusion/exclusion criteria.

8.2 Demographic and Baseline Variables

Demographic data and other baseline characteristics will be presented for the ITT set.

The following demographic and other baseline characteristics will be summarised and listed for this study:

- Age (years) - calculated relative to date of gene therapy
- Age group
 - 0 to <28 days
 - 28 days to <24 months
 - ≥24 months to 11 years
 - <11 years
- Age group 2
 - < 5 years
 - ≥ 5 years
- Sex
- Race
- Ethnicity
- Height (cm)
- Weight (kg)

- BMI (kg/m²)
- Body Surface Area (m²)
- Country of residence
- Time since diagnosis (years) - calculated relative to date of consent
- Derivations for demographic data are included below:
 - BMI (kg/m²) = weight (kg) / height (m)²
 - Body Surface Area (m²) = $\sqrt{\frac{\text{weight}(\text{kg}) \times \text{height}(\text{cm})}{3600}}$
- Busulfan cumulative AUC (note that busulfan will only be summarised in the conditioning regimen output [see Section 12] and will not be summarised with demographics):
If subject receives 8 doses of busulfan ($AUC1 + AUC6) \times 4$
If subject receives 9 doses of busulfan ($AUC1 + AUC6) \times 4 + \frac{AUC6 \times D9}{D5}$
Where $AUC1 = AUC(0-\infty)$ from first dose, $AUC6 = AUC(0-6 \text{ h})$ from 5th or 6th dose, D5 is the 5th dose and D9 is the 9th dose

A listing will also be created for the length of hospitalisation for gene therapy.

8.3 Medical Conditions

Medical conditions captured by the relevant Medical History page will be summarised for the ITT set and will be coded using MedDRA version 21.1 or higher. The version will be included in the footnotes of applicable outputs. A flag will be produced to indicate conditions which are ongoing at screening regardless of the onset dates of the medical conditions. They will be summarised by System Organ Class (SOC) and Preferred Term (PT). Relevant medical history will be both tabulated and listed.

Medical conditions of infections or bleeds collected in the 12 months prior to gene therapy that are equivalent to a CTCAE Grade 3, 4 or 5 events will also be summarised and compared to CTCAE Grade 3, 4 and 5 events that occur after gene therapy. See Section 10.2.2.1.

A Listing will be created of WAS condition at screening including WAS mutation, Baseline WAS Expression and WAS severity.

8.4 Prior and Concomitant Medications

Medications will be summarised for the ITT set and coded using the 1st September 2018 version of WHO-DD or higher. The version will be included in the footnotes of applicable outputs.

Concomitant medications excluding conditioning regimen and PBSC mobilisation will be summarised by treatment phase as defined in Table 2 in Section 5.3.5. The number and percentage of subjects receiving concomitant medications will be summarised based on ATC Level 1 codes.

Exposure to conditioning regimen (including pre-conditioning with rituximab and ATG Thymoglobulin, and reduced intensity conditioning with busulfan and fludarabine) will be summarised.

A summary of the terms included in these groupings is included in [Appendix 2](#).

See Section 7.3.1 for handling of partial dates for medications, in the case where it is not possible to define a medication as prior or concomitant, the medication will be classified by the worst case; i.e. concomitant.

Prior medication definition:

Prior medications are medications which are started and stopped prior to the gene therapy date.

Concomitant medication definition:

Medications will be labelled as concomitant medications if they satisfy both of the conditions below:

1. The medication is started prior to, on or after gene therapy.
2. The medication ended on or after the date of gene therapy or was ongoing at the end of the study.

Medications will be counted in all treatment phases (as defined in Table 2) for which they are ongoing.

Listings will be created for relevant previous medications at screening, concomitant medications by treatment phase, concomitant medications of special interest (for infections, eczema and autoimmunity) by treatment phase, PBSC mobilisation (including G-CSF and plerixafor) and condition medications.

8.5 Treatment Compliance

As gene therapy is likely to be administered once, compliance to study medication will not be presented.

8.6 Treatment Exposure

Exposure to study medication, which for this study is gene therapy, will be presented for the ITT set.

Exposure will be presented through summary statistics (n, mean, SD, median, min and max) of:

- Total volume infused (mL)
- Total nucleated cells (10^6)
- Number of nucleated cells/kg (10^6 /kg)
- CD34⁺ cells/kg (10^6 /kg)
- Number of CFU-GM (/ 10^6)
- Transduction Efficiency (CFU-C) (%)
- Vector copy number (VCN/cell)

Data on study medication exposure will also be listed. A listing will also be created of the stem cells collected.

9 Efficacy Analyses

As defined in the protocol, confidence intervals for proportions will be calculated according to the Wilson approach ([Brown, 2001](#)):

$$\left(\hat{p} + \frac{z_{\alpha/2}^2}{2n} \pm \frac{z_{\alpha/2} \sqrt{\left(\hat{p}(1 - \hat{p}) + \frac{z_{\alpha/2}^2}{4n} \right)}}{\sqrt{\frac{1 + z_{\alpha/2}^2}{n}}} \right)$$

Where \hat{p} is the proportion with the event, and n is total number and $z_{\alpha/2}$ is the $100 \left(1 - \frac{\alpha}{2}\right)$ percentile of the standard normal distribution. This can be calculated using the CL=WILSON option within the PROC FREQ procedure in SAS.

An exact Poisson procedure will be adopted for deriving CIs for incidence rates using the below formulas:

$$Y_l = \frac{\chi_{2Y, \alpha/2}^2}{2T} \text{ and } Y_u = \frac{\chi_{2(Y+1), 1-\alpha/2}^2}{2T}$$

Where Y is the observed number of events, Y_l and Y_u are the lower and upper confidence limits for Y respectively, $\chi_{\nu, \alpha}^2$ is the chi-squared quantile for the upper tail probability on ν degrees of freedom, and T is the person year time at risk.

Confidence Intervals for the means or mean changes in continuous variables will be derived with standard parametric methods, if appropriate. Otherwise medians with their corresponding confidence intervals will be presented.

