4.3. Efficacy Endpoints

4.3.1. Primary efficacy endpoints

a) Overall survival

From day +1 to 3 years after gene therapy, and then monitored as part of the long-term follow up.

b) Sustained engraftment of genetically corrected hematopoietic stem cells in peripheral blood and/or in bone marrow

Presence of gene corrected cells assessed by quantitative PCR on peripheral blood and bone marrow cells at 1 year after gene therapy. Adequate engraftment is defined as ≥ 0.04 VCN/cell in BM CD34+ (equivalent to 4% assuming a VCN of 1) or ≥ 0.1 VCN/cell in peripheral blood T lymphocytes (equivalent to 10% assuming a VCN of 1).

c) Expression of vector-derived WASP

Presence of detectable vector-derived WASP expression at 1 year after gene therapy by FACS analyses and/or Western Blot.

In case of failure of engraftment of transduced cells in two or more patients, intensification of conditioning dose and increase in the minimal cell dose will be considered after an amendment to the study.

d) Improved T-cell functions

Improvement in in vitro T-cell proliferation upon stimulation with anti-CD3i mAbs at 1, 2, and 3 years after gene therapy as compared to pre-gene therapy values.

e) Antigen-specific responses to vaccinations

- Ability to mount a protective humoral response to nominal antigens, including antibodies to at least 4 out of 5 T cell dependent antigens tested (Tetanus Toxoid, Diphtheria, Hepatitis B, Pertussis, Haemophilus B) measured after the end of the vaccination schedule (foreseen >1 year after gene therapy). In case results are available on $n < 5$ antigens, the rule of at least $n-1$ will be applied for defining success.

- Ability to mount a protective humoral response to unconjugated polysaccharide antigens (Pneumococcus), measured after the end of the vaccination schedule (foreseen >1 year after gene therapy).

- Positive cellular response to Tetanus Toxoid after vaccination, measured by *in vitro* proliferative response >1 year after gene therapy.

f) Improved platelet count and normalization of MPV

Sustained increase in platelet count compared to baseline during the 3 year follow up, analyzing the individual longitudinal profile, according to the planned follow up visit and including platelet counts collected for clinical reasons during follow up (in transfusion independent patients).

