12.4. Efficacy endpoints

Primary efficacy endpoints

Overall survival

The Kaplan-Meier estimate of survival at 3 years from gene therapy will be obtained, with 95% Confidence Intervals, based on deaths by any causes related to disease. Survival will be also monitored as part of the long-term follow up.

Sustained engraftment of genetically corrected haematopoietic stem cells in peripheral blood and/or in bone marrow

The percentage of subjects who present at one year after gene therapy with adequate engraftment defined as $\geq 4\%$ CD34+ in the bone marrow or $\geq 10\%$ in peripheral blood T lymphocytes will be estimated and the 95% Confidence Intervals (CI) of this proportion will also be calculated. The description of the longitudinal profile over time of the percentage of gene corrected cells on both bone marrow and peripheral blood might be included as additional information.

Expression of vector-derived WASP

The percentage of subjects who present at one year after gene therapy with detectable vector-derived WASP expression will be estimated, with 95% CI.

Improved T-cell functions

The mean change between the pre-gene therapy and the 1-year values of in vitro T-cell proliferation upon stimulation with anti-CD3i will be calculated, with 95% CI, if appropriate. The description of the longitudinal profile over time of the levels of the in vitro T-cell proliferation might be included as additional information. The degree of correction (reached at 1, 2 and 3 years from gene therapy) with respect to normal control levels will also be described.

Antigen-specific responses to vaccinations

The percentage of subjects who respond to vaccination (see Section 9.4) performed > 1 year after gene therapy will be estimated, with 95% CI.

Improved platelet count

The percentage of subjects who improved the level of platelet count at 1, 2 and 3 years after gene therapy compared to baseline, shifting from one category to the subsequent as defined in Section 9.5, will be estimated, with 95% CI. The relative mean change in platelet count with respect to pre-gene therapy value will also be given. The description of the longitudinal profile over time of the platelet count might be included as additional information.

Secondary efficacy endpoints

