Severe infections and bleeding events will be classified according to the time of occurrence relative to treatment as in the Table 3 below. This classification will be used in displays containing severe infections and bleeding events data only. For AE displays including severe infections and bleeding events, the treatment phases for AE data defined in Table 2 will be followed.

Table 3 Windowing for treatment phases; Severe Infections, Bleeding Events and hospitalisations

Assigned Study Day (Inclusive)		Visit Assigned
From	To	
-365	-1	Pre-treatment
2	183	0-6 months follow-up
184	366	6-12 months follow-up
367	731	1-2 Years Follow-up
732	1097	2-3 Years Follow-up
1098	2923	3-8 Years Follow-up
2924	End of study	>8 Years Follow-up
184	End of study	> 6 months Follow-up

Windowing will be applied to the data prior to any missing data calculations.

6 Sample Size

Given the low frequency of disease and the degree of novelty of the proposed experimental approach, we plan to treat overall 8 patients, in an estimated 5-year period.

7 General Considerations

All study patients will be included for evaluation until the earliest time point of the following: completion of a minimum of 5 years follow up in this study (TIGET-WAS) and transition to a separate OLTFU study, death, withdrawal or loss to follow up. Patients who, at 1 year after gene therapy, show absence of transduced cell engraftment in peripheral blood and bone marrow will be subsequently evaluated for safety aspects only.

At the end of the study, when all subjects have completed a minimum of 5 years follow up and transitioned to a separate OLTFU study, a final statistical analysis will be performed with all data available up to the transition to the OLTFU study, and a final clinical study report will be compiled.

The final analyses will be performed after all required database cleaning activities have been completed and final database freeze and database release has been declared by Data Management (DM).

The default significance level will be 5%; confidence intervals will be 95% and all tests will be two-sided. As this study is not powered all p-values and confidence intervals will be nominal.

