9.1.1 Overall Survival

Overall survival is defined as the time in days from gene therapy to date of death. Subjects alive at the end of follow-up or having not yet reached the defined follow-up phase will be censored at the latest time point for which vital status information is available. Follow-up will be defined as all data up to the data cut or end of study depending upon availability of data per patient.

The Kaplan-Meier estimate of survival for the entire duration of follow up will be obtained, with 95% confidence interval (CI) if there is any fatal event. The analysis results will be presented in a graph as well as a table. A listing of fatal events will be reported as a safety display.

9.1.2 Engraftment of genetically corrected hematopoietic stem cells in peripheral blood and/or in bone marrow

Adequate engraftment of genetically corrected cells in peripheral blood and/or in bone marrow is defined as ≥ 0.04 VCN/cell in bone marrow CD34 $^{+}$ or ≥ 0.1 VCN/cell in peripheral blood T Lymphocytes CD3 $^{+}$ at 1 year after gene therapy.

Missing PB CD3 $^{+}$ values will be imputed using the mean PB CD4 $^{+}$ and PB CD8 $^{+}$ values obtained from the same sample at that visit. If insufficient data are available to determine an adequate engraftment, the response will be set to missing. This includes two scenarios:

- Neither BM nor PB samples provides data for engraftment assessment;
- Values are below the threshold for the respective sample matrix (BLQ).

A summary table detailing the number and percentage of subjects who present with adequate engraftment at 1 year after gene therapy will be generated, with the 95% CI of the percentage calculated. PCR transduced cell evaluation in BM and PB will be summarised with descriptive statistics and graphs. Time to adequate engraftment will be plotted and listed based on VCN in BM and PB. The percentage of lentiviral vector (LVV) transduced colony forming units (CFU) in bone marrow cells (%LV in BM) will also be tabulated and plotted.

The longitudinal profile of the PCR transduced cell evaluation in BM and PB over time will be presented in a listing and a plot.

A box plot will be created for engraftment (PB CD3⁺ and BM CD34⁺ VCN/cell) by treatment source (BM or PB) at each year post gene therapy.

Scatterplots will be presented of treatment dose (CD34+/kg), busulfan dose (AUC), and age at treatment against engraftment (PB CD3⁺ and BM CD34⁺ VCN/cell) at each year post gene therapy.

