9.2.4 Bleeding episodes

Bleeding will be recorded on Relevant Medical History page, Concomitant Diseases page and Adverse Event page. Terms that will be considered for bleeding episodes are defined in [Appendix 2](#).

Bleeding episodes will be summarised and listed in the same way as severe infections.

A separate table and plot will be produced to summarise the bleeding episodes by severity and by SOC. Three severity categories will be used for the table: Mild for CTCAE grade 1, Moderate for CTCAE grade 2, and Severe for CTCAE grade 3 or above.

Summaries of severe bleeding events and moderate bleeding events will be created. Each summary will compare the pre-gene therapy phase with the post-gene therapy phase. Rate of events per patient year outcome will be presented along with accompanying confidence interval. A separate summary of the number and rate of bleeding events defined from Haemorrhages (SMQ) will be presented, by treatment phase and severity. All bleeding episodes will be listed.

A plot of the distribution of bleeding events by site (SOC) will be presented as pie charts representing each of the treatment phases defined in Table 2.

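### The SAP's written definition of the exact Poisson limits contradicts its formula (zero-event upper limit 146-fold too small), and the SAP omits the protocol's 3-year survival interval if nobody dies

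*SAP*

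**What the plan says.** **Rates.** SAP section 9 (Efficacy Analyses) adopts an exact Poisson procedure, as Protocol 12.5 does, and adds formulas. The lower limit is chi-squared on 2Y degrees of freedom with index alpha/2, divided by 2T. The upper limit is chi-squared on 2(Y+1) degrees of freedom with index 1-alpha/2, divided by 2T. Y is the event count and T the person-years at risk. The symbol, it says, "is the chi-squared quantile for the upper tail probability on" the given degrees of freedom. For the Wilson interval the same section names a SAS option; for the Poisson interval it names none. Rate intervals are planned for bleeding in SAP 9.2.4 ("Rate of events per patient year outcome will be presented along with accompanying confidence interval") and for hospitalisations in SAP 9.2.8.

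**Survival.** Protocol 12.4 states: "The Kaplan-Meier estimate of survival at 3 years from gene therapy will be obtained, with 95% Confidence Intervals". No condition is attached. SAP 9.1.1 says that the Kaplan-Meier estimate over all of follow-up "will be obtained, with 95% confidence interval (CI) if there is any fatal event", and it does not mention 3 years. SAP section 14, which lists changes to the protocol, does not record this one.

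**Which deaths count.** Protocol 12.4 describes the estimate as "based on deaths by any causes related to disease". Protocol 4.3.1 defines the endpoint with no restriction on cause: "From day +1 to 3 years after gene therapy, and then monitored as part of the long-term follow up". SAP 9.1.1 counts any death.

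**The concern.** The Poisson indices and the sentence that explains them cannot both be right, and a programmer or validator has no named software option to settle the matter. Crossed limits would probably be noticed. The zero-event cell is the risk: an upper limit close to zero looks like a good result and would suggest near-certainty that bleeding or hospital admissions had stopped. Zero counts are realistic when 8 patients are split across follow-up windows.

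Overall survival is the first-listed primary efficacy endpoint. Under the SAP, its most favourable outcome (no deaths) would be the one reported with no statement of uncertainty. In an unpowered, descriptive trial of 8 patients, the interval is the main thing that tells a reader how little the data can exclude.

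**Working it through.** The plan states no numerical Poisson limit and no survival limit, so there is no figure to reproduce. I evaluated the formulas under both readings.

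**Inputs.** Two-sided 95% intervals, alpha = 0.05 (SAP section 7). 8 patients (SAP section 6). Windows from SAP Table 3, "Windowing for treatment phases; Severe Infections, Bleeding Events and hospitalisations". I assume that all 8 patients are followed through each window:
- 0-6 months, days 2-183: 182 x 8 / 365.25 = 3.99, about 4 person-years
- 1-2 years, days 367-731: 365 x 8 / 365.25 = 7.99, about 8
- 3-8 years, days 1098-2923: 1826 x 8 / 365.25 = 39.99, about 40

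**Step 1: zero events.** The upper limit uses 2 degrees of freedom and index 0.975.
- Upper-tail reading, as the text defines it: quantile 0.0506, so the limit is 0.0506/(2T) = 0.0253/T.
- Lower-tail reading: quantile 7.378, so the limit is 7.378/(2T) = 3.689/T.
- Ratio: 7.378/0.0506 = 146 (145.7 before rounding), whatever T is.

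**Step 2: three events.**
- As defined: lower 14.449/(2T), upper 2.180/(2T).
- Correct: lower 1.237/(2T), upper 17.535/(2T).

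| T (person-years) | Y = 0 upper, as defined | Y = 0 upper, correct | Y = 3 lower / upper, as defined | Y = 3 limits, correct |
|---|---|---|---|---|
| 4 | 0.0063 | 0.922 | 1.806 / 0.272 | 0.155 to 2.192 |
| 8 | 0.0032 | 0.461 | 0.903 / 0.136 | 0.077 to 1.096 |
| 40 | 0.0006 | 0.092 | 0.181 / 0.027 | 0.015 to 0.219 |

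**Step 3: how general this is.** As defined, the limits cross for every Y checked from 1 to 5000. Coverage is zero once the expected count exceeds 0.0253. Under the lower-tail reading, direct Poisson tail probabilities are 0.025 on each side, and coverage was at least 95% at every mean tested. The printed indices are therefore sound, and the fault lies in the words that define them.

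**Step 4: survival with no deaths.** With n of n patients alive at 3 years, the exact (Clopper-Pearson) lower limit is 0.025^(1/n). The Wilson lower limit is n/(n + 3.841).

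| Patients followed to 3 years | Exact | Wilson |
|---|---|---|
| 8 | 63.1% | 67.6% |
| 7 | 59.0% | 64.6% |
| 6 | 54.1% | 61.0% |

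The last row corresponds to the first interim in SAP 7.4: "When the first 6 treated subjects complete 3 years of follow up after gene therapy". It counts only those 6 patients.

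**Step 5: one death in 8, no censoring.** S = 7/8 = 0.875, and the Greenwood sum is 1/(8 x 7) = 1/56.
- Plain Greenwood: 0.875 ± 1.96 x 0.875 x sqrt(1/56), which is 64.6% to 110.4%.
- Log-log: 38.7% to 98.1%.

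The plain interval exceeds 100%, and its lower limit (64.6%) is higher than the exact limit for no deaths (63.1%). The choice of Kaplan-Meier interval therefore has to be named along with the no-death rule.

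**The case against.** **On the Poisson limits.** The formulas as printed are the standard ones, the method is named, and the results are labelled lower and upper. A competent programmer would use a cumulative quantile and get correct limits. The same code also runs on the pre-treatment year and several follow-up windows, so crossed limits in cells with events would expose the mistake before a zero-event cell misled anyone. The endpoints are secondary, and SAP section 7 calls all intervals nominal. Equation layout may also have suffered in the PDF. Much of this stands as a statement about likelihood: correct code may already exist. It does not make the specification right. The faulty element is a readable sentence rather than a damaged symbol, and a document that governs programming and validation should not define its limits the wrong way round.

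**On survival.** With no deaths, the Greenwood interval collapses to 100%-100%, so the SAP arguably omits only an uninformative interval. Protocol 12.4 names no method that would avoid this. The full Kaplan-Meier curve passes through 3 years, and the separate table shells, which are not available, may contain a 3-year row. The collapse is real, but it is a reason to name another method, not to give no interval. A possible row in a shell does not restore an interval that the SAP makes conditional.

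**On the remedy.** Using a binomial method with no deaths and log-log with deaths switches method on the result. For 7 of 8 alive, Clopper-Pearson gives a lower limit of 47.3% and Wilson 52.9%, against 38.7% by log-log. Part of the drop from 63.1% therefore comes from the switch. That is fair, but the ordering stays sensible: one death never looks better than none.

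**Conclusion.** The concern holds. The SAP's definition of the Poisson quantile contradicts its own indices. Taken literally, it gives crossed limits for any non-zero count and a zero-event upper limit 146-fold too small. The ratio does not depend on follow-up; the per-year figures assume that all 8 patients are observed throughout each window. The harm arises only if code follows the written definition.

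For survival, the SAP departs without saying so from an unconditional protocol commitment on a primary endpoint. With 8 of 8 alive and followed to 3 years, the missing statement is a lower limit of 63.1% (exact) or 67.6% (Wilson), and it is lower still if fewer reach 3 years. Protocol 1.1.5 reports 89.1% 5-year survival for patients transplanted after 2000 in a 194-patient series, so a reader needs to see that limit beside an observed 100%.

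The wording on cause of death is a minor inconsistency. The SAP already counts every death, so no planned output changes. The first two points should be corrected before the final analysis.

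**What to change.** - **SAP section 9:** define the index as a lower-tail (cumulative) probability. Set the lower limit to 0 when Y = 0, because chi-squared on 0 degrees of freedom is undefined. Describe the limits as those of the rate Y/T, since the formulas divide by T.
- **SAP 9.1.1:** name the 3-year estimate and always give a 95% interval. If there are deaths, use the Kaplan-Meier interval with the log-log transformation. If there are none, use the exact binomial interval (or Wilson, already the plan's method for proportions) on the patients followed to 3 years. Choose one of the two in advance. State that number and list anyone censored earlier.
- **SAP section 14:** record the survival change and state that all deaths count. Align Protocol 12.4 to death from any cause at the next amendment; this can wait once SAP 14 records the definition.

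The cost is a few SAP sentences and a few lines of code, with no new data. There are two downsides. The intervals will look less favourable. The no-death interval also ignores partial follow-up from patients censored before 3 years, for example after an allogeneic transplant or loss to follow-up (Protocol 5.1.4.1).
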